**Figure 3. Flow Sorting and phenotypic subset analysis of donor reactive clones.**  
Bulk MLRs were prepared and the cellular makeup of responder cell populations were delineated after 7 days in culture using fluorochrome coupled monoclonal antibodies. The cells were analyzed first by gating on lymphocytes and then after gating on CFSE diluted proliferating responder cells. The CFSE diluted donor reactive T cells were sorted for ImmunoSEQ analysis.

CD3+CD8+ cell subsets are sorted out separately and is shipped to Adaptive Biotechnologies in Seattle.

**ImmunoSEQ analysis of donor-reactive T cells:** At Adaptive Biotechnologies total genomic DNA is purified from the flow-sorted CD3+CD4+ and CD3+CD8+ cell subsets from each culture using Qiagen DNeasy Blood extraction Kit following the manufacturer's protocol. Then, a multiplex PCR assay that is capable of specifically amplifying rearranged TCRB genes from a complex background followed by deep sequencing is performed (**Figure 4**).

The data is analyzed measuring clonality, proportion and diversity of the T cell repertoire (18-20). These represent the total T cell repertoire the recipient is capable of reacting to the donor. We have denoted the performance of the pre-transplant MLR, isolation of donor reactive clones and ImmunoSEQ analysis, collectively as **AlloSEQ**.

**Figure 4. TCR $\beta$  sequencing assay.**  
**(A)** The assay is designed to identify the V D and J segments in recombined CDR3 TCR $\beta$  genes  
**(B)** Forward primers were designed to amplify all 45 TCR $\beta$  V segments. Reverse primers were designed to each of the 13 TCR $\beta$  J segments.  
**(C)** Custom software tools have been developed to verify, collapse, align and catalog the CDR3 sequences for calculation of repertoire diversity.

## ***Enumeration of donor reactive T cell clones in post-transplant kidney biopsies, blood and urine:***

[figure not shown]
The transplant biopsy represents a sampling of the allograft and rejection is manifested as cellular infiltration, mostly of donor reactive T cells and B cells, classically detected through immunohistopathological staining and microscopic examination. An alternate approach that we have developed is to monitor the graft for infiltrating donor-reactive clonotype identified through AlloSEQ (17). This would entail isolation of total genomic DNA from the biopsies, performance of immunoSEQ analysis as above and monitoring for the presence and copy number of donor-reactive clones identified through the pre-transplant AlloSEQ, and then correlating with the severity of rejection monitored through immunohistopathological examinations.

We had proposed that transplant rejection can more easily be diagnosed through the sampling of the urine pellet or peripheral blood for clonal frequency and abundance of donor-reactive T cells pre-identified through AlloSEQ. This is to monitor rejection in a non-invasive manner.

We have already established the technology (17) and other investigators have used it to show that donor reactive clones are reduced or deleted in tolerant kidney transplants (21). Therefore, these proposed studies monitoring post-transplant graft rejection or its absence can be greatly leveraged to innovatively assess the relative efficacies of the drugs being compared.

## Analysis of HLA and Donor-Specific B cells

Measurement of B cells in the peripheral blood with potential to make HLA antibodies against graft donor antigens might provide a way of analyzing antibody formation and shed light on the balance between production, inhibition and sequestration at any given time in the post-transplant period. Perry and coworkers have recently reported HLA antibody production in vitro by B cells from the bone marrow of sensitized kidney transplant recipients. T and B-cell ELISPOT have also been used to measure HLA specific B cell frequency against a given antigen. ELISPOT assay does not measure the frequency of cells that actually bind the antigen and only measures biological events such as cytokine release or production of immunoglobulin after differentiation in vitro. Furthermore, the estimated frequency is restricted to the cells that are able to be selectively stimulated by the antigen depending on read-out and thus may lead to an underestimation of the actual frequency of committed cells. Another approach based on the structural similarity between B cell receptor and immunoglobulin binding sites, it is postulated that HLA-specific B cells (HSB) should bind to HLA molecules with specificity comparable to that of the secreted immunoglobulin. Identification of HLA specific B cells by staining through binding of the B cell receptor using fluorescently labeled tetramers of identified HLA class I specificities has been described. A solid-phase assay utilizing

[figure not shown]
## Northwestern University Feinberg School of Medicine: Extended-Release Tacrolimus Vs. Twice-Daily Tacrolimus

color-coded microspheres, each coated with a unique HLA antigen has become the main multiplex assay used for the detection of allo-specific antibodies against donor antigens. Its multiplexing power enables the analysis of the antibodies directed to all available synthetic HLA class I and class II alleles in one assay. Utilizing these single antigen HLA beads (SAB) Degauque et al. described a novel assay to identify HLA-specific B cells in transplant recipients (22). We have further developed this novel multiplex bead-based assay to identify HSB (schematically described in **Figures 5 and 6**), and propose here to study the circulating HSB in kidney transplant recipients with chronic AMR.

*Figure 5: Assay Design*

Proposed studies:

1. Frequency of Donor-specific B cells (DSB) by Novel HLA Bead Multiplex Assay: We will analyze the serial samples of peripheral blood mononuclear cells (PBMC) using our novel HLA-bead multiplex assay to identify and determine the changes in frequency of total B, HLA-specific B (HSB) and DSB cells in KT recipients with cAMR in each study arm.

*Figure 6: Analysis Strategy*

2. Immunophenotyping of HLA-specific B cells and Donor-Specific B cells by Flow Cytometry: We will analyze serial samples of PBMC, before and at 3 and 12 months post-transplant, using multi-parameter flow-cytometry for immunophenotyping of (i) total B, HSB and DSB cells with surface expression of IgD, CD24, CD27 and CD38.

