### **Inclusion Criteria:**

1. Patients who are males or females aged 18-65 years.
2. Donors aged 18-65 years.
3. No prior organ transplant
4. Patients who are single-organ recipients (kidney only).
5. Women who are of childbearing potential must have a negative serum pregnancy test before transplantation and agree to use a medically acceptable method of contraception throughout the treatment period.
6. Subject (recipient) is able to understand the consent form and give written informed consent

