### **Exclusion Criteria**

1. Delayed graft function (please see above).
2. Known sensitivity or contraindication to alemtuzumab, Envarsus® XR, tacrolimus or MMF.
3. Use of the following induction medications: basiliximab and rituximab.
4. Patient with significant or active infection.
5. Patients with a positive flow cytometric crossmatch using donor lymphocytes and recipient serum.
6. Patients with PRA > 40%
7. Patients with current or historic donor specific antibodies
8. Body Mass Index (BMI) of < 18 or > 35
9. Patients who are pregnant or nursing mothers.
10. Patients whose life expectancy is severely limited by diseases other than renal disease.
11. Ongoing active substance abuse, drug or alcohol.
12. Major ongoing psychiatric illness or recent history of noncompliance.
13. Significant cardiovascular disease (e.g.):
  - a. Significant non-correctable coronary artery disease;
  - b. Ejection fraction below 30%;
  - c. History of recent myocardial infarction.
14. Malignancy within 3 years, excluding non-melanoma skin cancers.
15. Serologic evidence of infection with HIV or HBVs-Ag positive.
16. Patients with a screening/baseline total white blood cell count < 4,000/mm^3; platelet count < 100,000/mm^3; triglyceride > 400 mg/dl; total cholesterol > 300 mg/dl.
17. Investigational drug within 30 days prior to transplant surgery.
18. Anti-T cell therapy within 30 days prior to transplant surgery.

*Northwestern University Feinberg School of Medicine:* Extended-Release Tacrolimus Vs. Twice-Daily Tacrolimus

19. Diagnosis of atypical-Hemolytic Uremic Syndrome (aHUS).
20. Subjects transplanted with a Hepatitis C NAT-positive kidney.

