## **STUDY TIMELINES:**

We expect the total duration for this study not to exceed 2 years from the date of the last subject's enrollment. Each individual subject will be part of the study for 12 months after transplantation.

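### The donor-specific B-cell frequency analysis is limited to recipients with chronic AMR, a group the trial neither enrols nor defines and that is likely to be too small for an informative by-arm comparison

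*Combined protocol and SAP*

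**What the plan says.** Under Procedures Involved, Analysis of HLA and Donor-Specific B cells, the authors describe their bead assay for HLA-specific B cells (HSB) and "propose here to study the circulating HSB in kidney transplant recipients with chronic AMR". Proposed study 1 repeats the limit: serial samples will be used to "determine the changes in frequency of total B, HLA-specific B (HSB) and DSB cells in KT recipients with cAMR in each study arm". DSB are donor-specific B cells.

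Proposed study 2, immunophenotyping of total B, HSB and DSB cells, carries no such limit in its own wording: "We will analyze serial samples of PBMC, before and at 3 and 12 months post-transplant". The Blood Immunophenotyping section uses the same three time points, also unrestricted.

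The cohort is described elsewhere:
- Inclusion Criteria: "No prior organ transplant".
- Exclusion Criteria: "Patients with current or historic donor specific antibodies" and "Patients with a positive flow cytometric crossmatch using donor lymphocytes and recipient serum". PRA above 40% is also excluded.
- Number of Participants: 25 per arm.
- Study Timelines: "Each individual subject will be part of the study for 12 months after transplantation".

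Neither Study Endpoints nor Statistical analysis mentions chronic AMR. The rejection endpoint in the statistical plan is acute rejection.

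**The concern.** Proposed study 1 is written for a population that this trial does not recruit. A recipient can enter that group only by developing cAMR after transplantation, in effect after randomisation and within a 12-month window. No definition of cAMR, expected number of cases or analysis for the group is given.

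Two consequences follow. First, the group may hold so few recipients that nothing useful can be said by arm. Second, the Objectives and Hypothesis section posits less immunologic allograft injury with the once-daily formulation. cAMR is an injury of that kind, so selecting on it means selecting on something treatment may change. The recipients with cAMR in the two arms need not be comparable, and randomisation would no longer protect the contrast.

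There is also a practical problem. A laboratory following the section cannot tell whose samples go into the frequency assay, since the two proposed studies appear to name different populations for the same cells.

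**Working it through.** **The plan's own figures.** The documents state no number for a cAMR group. The only power figures (Sample size and power) are 0.82 and 0.99 for effect sizes 1.0 and 2.0 with 25 per arm, two-sided alpha 0.05, and they concern whole arms. A two-sample t test with those settings gives 0.934 for effect size 1.0 (0.900 with 22 per arm) and more than 0.99 for 2.0. The 0.82 is therefore not reproduced, but that is a separate matter and nothing below depends on it.

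**Inputs.** n = 25 per arm (Number of Participants). About 22 per arm remain after the assumed 10% attrition (25 × 0.9 = 22.5). The 12-month cAMR rate p is an assumption, varied from 1% to 20%.

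**Formulas.** The number of cases per arm is X ~ Binomial(25, p), independent between arms.
- Expected cases per arm: 25p.
- Chance that at least one arm has no case: 1 − [1 − (1 − p)^25]².
- Chance that both arms have at least 2 cases: [P(X ≥ 2)]².

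Example at p = 5%: 0.95^25 = 0.277, and 1 − (1 − 0.277)² = 0.48.

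| Assumed rate | Expected per arm | At least one arm empty | At least 2 in both arms |
|---|---|---|---|
| 1% | 0.25 | 95% | 0.1% |
| 2% | 0.5 | 84% | 0.8% |
| 5% | 1.25 | 48% | 13% |
| 10% | 2.5 | 14% | 53% |
| 20% | 5 | 0.8% | 95% |

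With 22 per arm at 5%, the values are 1.1 expected, 54% and 9%.

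**Power if the group is not empty** (two-sided t test, alpha 0.05):

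| Cases per arm | Effect size 1.0 | Effect size 2.0 |
|---|---|---|
| 2 | 0.10 | 0.22 |
| 3 | 0.16 | 0.46 |
| 5 | 0.29 | 0.79 |

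For 80% power, 17 cases per arm are needed at effect size 1.0. That is a cAMR rate of 17/25 = 68% to 17/22 = 77%. At effect size 2.0, 6 per arm are needed, a rate of 6/25 = 24% to 6/22 = 27%.

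**Selection.** This point needs no rate. If treatment alters who develops cAMR, the two cAMR groups are different selections from the randomised arms, however many recipients they contain.

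**The case against.** Several points on the other side are fair.

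- **No rate is given.** That the eligibility rules and 12-month follow-up make cAMR rare is clinical background, not a statement in the documents. A reader might infer that the group will be nearly empty and the comparison impossible. The documents do not support that: at an assumed 10%, 2.5 cases per arm are expected and an empty arm has only a 14% chance. What stands is that the comparison is unlikely to be informative, since even 5 per arm gives power of 0.29 at effect size 1.0.
- **Item 2 covers the same cells.** A reader might infer that item 1 is the only donor-HLA-specific B-cell work in the trial. It is not: item 2 phenotypes HSB and DSB cells at all three time points without the limit.
- **No named endpoint depends on it.** HSB/DSB frequency does not appear in Study Endpoints, in the primary hypothesis or in the power statement. General B-cell phenotyping is unrestricted, and DSA is assessed separately as a secondary endpoint.
- **The by-arm wording may be descriptive.** No between-arm test of HSB/DSB frequency is specified, and the selection argument applies only if the arms are contrasted. But the statistical section does plan to compare trajectories of cell populations, and a within-arm description of about one recipient would say little either.
- **It is a pilot.** The plan waives power for secondary outcomes. That excuses small numbers, but does not explain a population that matches neither the enrolled cohort nor item 2.

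**Conclusion.** The mismatch is in the text itself, stated twice, and does not depend on any assumed figure: item 1 and the sentence of purpose before it name a population that the rest of the plan neither recruits nor defines, and item 2 does not share the limit. The likely size of the group does rest on an assumed rate. Up to about 5% it would be roughly one recipient per arm or fewer; at 10% to 20% it would be 2.5 to 5, not empty but still small. The loss of randomised comparability holds at any rate, provided treatment affects cAMR as the study hypothesises for immunologic injury.

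The consequence is limited to the exploratory item 1 frequency readout. It would be tempting to say that objective 2 or the immune-activation primary endpoint is compromised; the documents do not support that, because the B-cell work named there is unrestricted. This assumes that item 2 is read on its own wording and is not governed by the preceding chronic AMR sentence, which is a further reason to correct that sentence. The text should be amended, but the trial's main analyses do not turn on it.

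**What to change.** In Proposed studies item 1, replace the cAMR restriction with: *in all randomised recipients in each study arm, before transplantation and at 3 and 12 months*. Change the preceding chronic AMR sentence in the same way, so that both agree with item 2 and with Blood Immunophenotyping. State that any recipient who develops AMR will be reported descriptively, with the definition of AMR given.

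This is a wording amendment with no change to treatment or visits. The by-arm analysis would then draw on 25 recipients per arm, about 22 after attrition, instead of about one per arm at an assumed 5% rate. The cost is additional bead-assay runs on PBMC samples already planned: at most 50 recipients × 3 time points = 150 samples, fewer with attrition. The documents give no assay cost or cell yield, so the sponsor should confirm that this is feasible.

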## DATA AND SPECIMEN BANKING:

Samples collected will be banked at the Immune Monitoring Core (IMC) (under the leadership of Co-I [name]) of the Comprehensive Transplant Center (CTC) of Northwestern University. The blood immunophenotyping will be performed prospectively on fresh samples. The pre-transplant donor-specific MLR and flow-sorting of reactive T cells will also be performed with fresh samples. Cell pellets thus obtained (for AlloSEQ analysis) as well as post-transplant PBMC, urine sample pellets and biopsies will be frozen and sent blinded (**de-identified**) to Adaptive Biotechnologies, Seattle for DNA purification and ImmunoSEQ analyses. Leftover

*Northwestern University Feinberg School of Medicine:* Extended-Release Tacrolimus Vs. Twice-Daily Tacrolimus

samples of biopsies (paraffin-block after IHC staining), PBMC and urine pellets will be used for RNA isolation and gene expression profiling in a future study.

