## **NUMBER OF PARTICIPANTS:**

Prospective randomized single center open label study of 2 groups of kidney transplant patients

- Group 1 : standard of care (SOC) control group will receive tacrolimus twice-daily (n=25)
- Group 2 : LCP-Tacro/Envirox® XR group will receive LCPT tablets once daily (n=25)

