## **STUDY ENDPOINTS:**

### **Primary endpoints:**

One of the 2 primary end points Kidney transplant function assessed as kidney injury markers in urine samples collected at 12-hour and 24-hour trough levels and 2-hour peak levels at 2nd week, 3rd month, 12th month post transplantation, and at any for-cause biopsy event. The injury markers will be assessed using Myriad-RBM KidneyMAP panel <https://myriadrbm.com/products-services/humanmap-services/kidneymap/>.

The other primary end point is immune activation assessed through serial flow cytometric immunophenotyping for immune cells including T and B cell subpopulations as well as donor-reactive TCR repertoire analysis in biopsy, blood and urine.

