## RESOURCES AVAILABLE:

Successful completion of the project requires the following: **a) Team of dedicated investigators:** Drs. [name] and [name] are transplant nephrologists and [name] is a transplant surgeon and they have dedicated their careers to translational research to refine the management of renal transplant recipients. They will actively recruit all patients and, assisted by an RN research coordinator at the CTC, perform all of the clinical assessments in this cohort. They will maintain the clinical database with help from the assistant coordinators. They will work closely with the co-I, [name] and his trained technologists in the Immune Monitoring Core of the CTC performing and interpreting the assays. [name] will perform the statistical analysis of the immunophenotyping and [name] will interpret the biopsies and IHC staining. Northwestern has formed a collaborative partnership with Adaptive Biotechnologies, Seattle for ImmunoSEQ analyses to identify TcR repertoire usage in donor-specific immune responses. A similar partnership has been established with Myriad-RBM for the analysis of kidney injury markers using their KidneyMAP panel, **b) Ideal patient population:** The Northwestern CTC transplant center provide the ideal infrastructure and performs a high number (>220) of living and deceased donor kidney transplant procedures/year to conduct this prospective trial and to analyze fresh patient samples. This readily supports recruiting 50 patients within one year enrollment period, even when considering the inclusion/exclusion criteria and other concurrent studies; **c) Institutional support:** [name], division head of the CTC will provide the full infrastructural support to conduct all clinical and laboratory portions of the study. In summary, the investigators, patient availability, and environment afford the highest chance of success in this proposal.

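### No masking to arm is stated for in-house flow gating (part of a primary endpoint) or for biopsy reading, although the trial is open label and both readings involve judgement

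*Combined protocol and SAP*

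**What the plan says.** All references are to the combined protocol and SAP.

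- **Design.** NUMBER OF PARTICIPANTS describes a "Prospective randomized single center open label study of 2 groups of kidney transplant patients", with 25 per arm.
- **Flow as a primary endpoint.** Under Primary endpoints: "The other primary end point is immune activation assessed through serial flow cytometric immunophenotyping for immune cells including T and B cell subpopulations". The same item adds donor-reactive TCR analysis. The Statistical analysis section again lists T and B cell subpopulations as primary.
- **How flow is done.** DATA AND SPECIMEN BANKING: "The blood immunophenotyping will be performed prospectively on fresh samples". RESOURCES AVAILABLE places the work with a co-investigator and "his trained technologists in the Immune Monitoring Core of the CTC performing and interpreting the assays".
- **Biopsies.** Under Secondary endpoints, biopsies at months 3 and 12 are compared between arms for CNI toxicity. RESOURCES AVAILABLE says that one team member "will interpret the biopsies and IHC staining".
- **Where blinding is stated.** DATA AND SPECIMEN BANKING says that sorted cell pellets and "post-transplant PBMC, urine sample pellets and biopsies will be frozen and sent blinded" to the sequencing company. SETTING repeats this. Both places explain blinded, in brackets, as de-identified.
- **Expectation.** Stopping Rules expects the listed infections to be fewer in the experimental arm. RISKS TO PARTICIPANTS anticipates less nephrotoxicity with LCP-tacrolimus. POTENTIAL BENEFITS TO PARTICIPANTS expects less nephrotoxicity and less immune activation.

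**The concern.** In an open-label trial, protection against expectation in the readings has to come from masking the people who read the assays. The plan writes that protection down for one outside laboratory and is silent for the two in-house readings that depend most on judgement: setting gates for small T and B subsets, and grading CNI toxicity on biopsy. A team could follow the plan exactly and still make both readings with the allocation in view.

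A shift of this kind looks the same as a treatment effect. The planned mixed models, covariate adjustment and imputation cannot separate the two. The shift would also spread: the Statistical analysis section correlates cell subsets with immunohistopathology and compares those correlations between arms, so bias in either reading enters that analysis too.

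**Working it through.** **Step 1: set the readings side by side.**

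| Reading | Endpoint | Where read | Masking stated |
|---|---|---|---|
| TCR sequencing (clonal repertoire) | Primary; the immune outcome that is powered | Outside laboratory | Yes, as de-identified |
| Urine injury-marker panel | Primary | Outside partner | None stated |
| Flow immunophenotyping | Primary (cell-subset part) | Investigators' own core | None stated |
| Biopsy and IHC | Secondary | Team member | None stated |

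De-identification removes the patient's identity. It does not by itself hide the arm. For example, the Kidney transplant function section collects trough urine at 12 hours in one arm and 24 hours in the other, so a label giving the trough time would reveal the arm on a de-identified tube.

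**Step 2: how much a reading shift would matter.** The plan gives no figure for reader bias, so there is none to reproduce, and its power figures do not enter this check.

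Inputs:
- n = 25 per arm (NUMBER OF PARTICIPANTS).
- n = 22 per arm after the assumed 10% attrition (Sample size and power): 25 × 0.9 = 22.5, rounded down.
- Two-sided α = 0.05 (Sample size and power).
- Shift b = 0.1, 0.2 or 0.3 SD between arms with no true effect. This is an assumption; the documents give no value.

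Normal approximation: δ = b / √(2/n), and the rejection rate is Φ(−1.96 + δ) + Φ(−1.96 − δ).

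Example with n = 25 and b = 0.2: √(2/25) = 0.2828, so δ = 0.707. The rate is Φ(−1.253) + Φ(−2.667) = 0.1051 + 0.0038 = 0.109.

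The Statistical analysis section names t-tests, so the same rate was also computed from the noncentral t distribution with 2n − 2 degrees of freedom and noncentrality δ.

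| Shift b | n = 22, normal | n = 22, t-test | n = 25, normal | n = 25, t-test |
|---|---|---|---|---|
| 0.1 SD | 6.3% | 6.2% | 6.4% | 6.4% |
| 0.2 SD | 10.2% | 9.9% | 10.9% | 10.7% |
| 0.3 SD | 16.9% | 16.3% | 18.5% | 18.0% |

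Over both methods and both sample sizes the ranges are about 6%, 10-11% and 16-19%. A 0.2 SD shift roughly doubles the nominal 5%, and nearly all of the excess falls in the favoured direction (10.3 of the 10.7 percentage points for the t-test at n = 25).

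**The case against.** The strongest case on the other side has five parts.

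1. **Silence is not unmasking.** A reader might infer that the technologists and the pathologist will know the arm. The documents do not say so; they say nothing either way. This stands, and the point is therefore that no masking is stated. It remains a gap, because masking that is not written down cannot be relied on or reported.
2. **The powered immune outcome lies elsewhere.** The primary hypothesis is framed on donor-reactive clones, and the power statement refers to change in the T cell clonal repertoire. Both rest on outside sequencing, and the in-house sort that precedes it uses cells taken before transplantation. The urine panel is also run outside. A reader might infer that the whole immune primary endpoint is compromised; the documents do not support that. The exposure is limited to the cell-subset part and to histology, which is secondary and expressly not powered in a pilot.
3. **Gating is partly constrained.** The antibody panels are fixed in advance, and Tube 1 of Table 1 is an IgG control in every channel. This limits judgement on whole blood but does not end it, and Table 2 lists no such tube.
4. **The shift is hypothetical.** No single flow subset is named as primary, many are listed, and a uniform shift in one agreed direction across all of them is not very plausible. This stands: the table in the working illustrates and does not estimate.
5. **Histology could be re-read.** DATA AND SPECIMEN BANKING mentions leftover paraffin blocks, so a later masked reading may be possible. However, that section assigns leftovers to a future gene-expression study, while SETTING expects them to be discarded. Re-reading is not something the plan secures.

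**Conclusion.** The point holds in a limited form. Masking is stated only for the sequencing shipments. None is stated for in-house flow gating or for biopsy reading, and both are open to bias in a trial whose protocol records the direction it expects. The size of any bias is unknown. The error rates of about 6%, 10-11% and 16-19% rest on assumed shifts of 0.1, 0.2 and 0.3 SD, a single comparison, no true effect and 22-25 readings per arm.

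A reader might also infer that codes already in use would remove the problem. The documents do not support that. They describe no specimen code: one is only implied by the de-identified shipments and by the identifier-free eCRF. A code without withheld allocation would not mask a reader in any case. The change below is a cheap improvement worth making before readings begin; it affects neither the sample size nor the significance level.

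**What to change.** Add to DATA AND SPECIMEN BANKING and to RESOURCES AVAILABLE:

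- Flow samples and study biopsy slides carry a study code only. Labels and request forms omit the arm and any arm-specific trough timing.
- The technologists who gate, and the pathologist who records the research biopsy assessment, do not see the allocation.
- Codes are linked to arm only after each assay result is locked.

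The same staff read the same samples, and no second reader is needed. Fresh samples are no obstacle, since a fresh tube can carry a code. The standard-of-care clinical reading of the biopsy is unaffected.

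The cost is protocol wording, a small coding step, and an order of work in which the research biopsy assessment is recorded before the treatment record is opened. The documents define no separate research assessment of the biopsy, so that would have to be specified. The change reduces reader bias but does not guarantee its removal.
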